Per FDA feedback, manikin testing will be performed to evaluate for potential interference of the SureCRIC with representative cricothyrotomy kits and tools, and to assess SureCRIC usability with these kits and tools. FDA agreed that the study results could be extrapolated to the following users and use cases: (a) intended user population including those who are more highly trained and experienced at performing cricothyrotomy; and (b) the tracheotomy procedure where the same anatomic landmarks are identified and the procedure is performed in less chaotic, in-hospital environments. Fifteen representative pre-hospital (novice) users and two representative experienced users will complete the cricothyrotomy procedure using three different representative cricothyrotomy kits for a total of 51 manikin testing scenarios. The cricothyrotomy kits will allow the participant to perform the cricothyrotomy procedure on the manikin via (a) the direct percutaneous access approach, (b) the Seldinger approach, and (c) the direct scalpel incision approach.

Participants in the study will complete study sessions that will consist of: 1) signing of necessary documents and pre-evaluation interview; 2) SureCRIC training (SureCRIC group only); 3) decay period (SureCRIC group only); 4) testing; 5) semi-structured interviews and critical error debriefing; 6) completion of knowledge tasks and labeling validation (SureCRIC group only); and 7) compensation arrangement.

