## 2 Purpose of the Study

Overall validation study objectives are:

- To measure SureCRIC effectiveness with regard to the intended use of helping to identify anatomical landmarks
- To demonstrate that SureCRIC can be used by representative users under simulated conditions with minimal critical errors
- To evaluate the effectiveness of user training and instructional materials

The human validation study is one of two parts of the final evaluation method intended to demonstrate the safety and effectiveness of the device, labeling and related materials (e.g., materials, packaging, labeling). From the human factors perspective, the validation study serves to ensure that risks associated with the use of a medical device have been identified and adequately addressed, and that the impacts of residual risks are minimized. InnoVital Systems, Inc. (InnoVital) has engaged the National Center for Human Factors in Healthcare (Human Factors Center) to conduct the validation (also referred to as summative) study for the SureCRIC. Validation conducted by the Human Factors Center will focus on evaluating the use of the device by its intended users in simulated use environments. Specifically, the objectives of the human evaluation are:

- Primary endpoint: pass/fail assessment for CTM identification. The use of ultrasound to predefine / pre-mark CTM boundaries on the skin was discussed in the pre-submission supplement meetings. However, internal testing suggests that skin movements with SureCRIC use, and small head and neck movements by subjects may cause the pre-marked skin to shift and result in inaccurate assessments. This finding is in line with the limitations reported in a recent study evaluating CTM identification success in conscious human volunteers [Lamb 2015]. For the purposes of the current study, and as discussed with FDA, an expert in neck / airway anatomy (e.g., otolaryngologist or trauma surgeon) will palpate the area to verify accurate CTM localization.
- Secondary endpoints: time to CTM identification will be measured for descriptive statistics only per FDA request. Additionally, medics will be asked to report their confidence in accurate CTM identification (e.g., on a visual analog scale). Preparticipation, post-training, and post-participation human factors data will also be collected, as well as data from labeling validation.

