# 5 Vulnerable Subjects.

Though not specifically planned or expected, it is possible that hospital / health system employees will be included as participants. No hospital or health system employees will be included as subjects. Participants and subjects will be protected in two ways. First, no identifying information will be recorded during the study, except for faces of the participants, subjects, and study investigators. Third-party recruiters and administrative staff will coordinate logistics of participants and subjects; therefore, researchers do not need or have access to participants' and subjects' phone numbers or emails. Once participants and subjects have signed their respective consent forms, there will be no connecting information between the person and their participant number or subject number. The data that is collected and analyzed will not contain any identifiers regarding subject name, date of birth or any other identifiers. Secondly, the recruitment material and information letter will make it explicitly clear that participants and subjects are free to end participation at any point in the study.

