- 3. Decay Period (minimum 60 minutes Experimental Group only). After training, Experimental group participants will be removed from the facility for a minimum of 60 minutes. Participants will then report to the testing facility at an agreed-upon time.
- 4. Testing (approximately 30 minutes). Prior to the participants returning to the test facility, the expert confirmer may, at his/her discretion, palpate the neck surface anatomical landmarks of the subjects to familiarize himself/herself with the anatomy. An ultrasound machine will be available to help the expert confirm anatomical landmarks if desired. Subjects may also have neck measurements taken (e.g., neck circumference and length). The verifier may also place a popsicle stick on the neck to indicate the position of the cricothyroid membrane. Pictures of the neck may be taken.

  After returning to the testing facility, Experimental Group participants will utilize the SureCRIC to perform various scenarios. Control Group participants will utilize a freehand approach to perform various scenarios. Subjects will be positioned supine with their necks in the neutral position consistent with standard practice for trauma patients. Testing is the only portion of the study where subjects will be involved.

During each scenario, participants will identify the CTM on one of the six subjects. Control Group participants will perform CTM identification freehand and Experimental Group participants will use the SureCRIC as an aid in CTM identification. Participants will be made aware that they will be timed prior to testing.

Once the participant has identified the CTM, he/she will gently place a popsicle stick with smooth, round edge on the CTM. The expert verifier will then take control of the stick. The SureCRIC, if used, will then be carefully disassembled with the stick in place. Pictures of the stick on the skin may be taken with the popsicle stick on the neck. The expert verifier will palpate the structures of the anterior neck to confirm accurate CTM localization. In the Experimental Group, the SureCRIC device may be gently and intentionally shifted in position by the verifier as he/she palpates the neck. The expert verifier will indicate to the NCHFH staff (but not the participant) whether the popsicle stick is at the level of the CTM and at the midline of the neck.

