After each CTM identification, the participant will report their confidence in accurately identifying the CTM. A slight modification to the procedure described by Lamb [2015] may be used, employing a 10-cm horizontal visual analogue scale (VAS) ranging from "very confident" (0) to "not at all confident" (10).

Only one subject will be available for CTM identification at a time though ultimately each participant will palpate each subject's neck, serially. The medic will not be informed of the success or failure of their identification attempt until the end of their involvement in the study. CTM identification attempts may be recorded for off-line analysis as needed.

Scenarios will include the following:

- Scenario #1: CTM identification of Subject 1 (with or without SureCRIC)
- Scenario #2: CTM identification of Subject 2 (with or without SureCRIC)
- Scenario #3: CTM identification of Subject 3 (with or without SureCRIC)
- Scenario #4: CTM identification of Subject 4 (with or without SureCRIC)
- Scenario #5: CTM identification of Subject 5 (with or without SureCRIC)
- Scenario #6: CTM identification of Subject 6 (with or without SureCRIC)

Each session will be observed by at least one Human Factors Center moderator, who will only be present to observe and give instructions and will not help participants with task completion in any way. Audio and video recording will be utilized for post-hoc data analysis. NCHFH staff will observe each CTM identification procedure focusing on procedural performance and usability in both user groups. NCHFH staff will additionally observe performance of critical tasks and essential tasks.

- 5. Semi-structured Interviews and Critical Error Debriefing (~15 minutes). Human Factors Center moderators will follow up with participants on any critical errors, close calls, or confusion/difficulty observed during task completion to determine the participant's perspective on the root cause of the error(s). Feedback will also be collected regarding perceived difficulty and usability of the device and IFU for the Experimental Group. Also for the Experimental Group, time is allotted for the moderator to ask the participants open-ended questions regarding their overall impressions of the SureCRIC, whether any tasks were particularly difficult to perform, whether training was adequate and how it might be improved, use of instructions during testing, and thoughts about SureCRIC use in the field.

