- 6. Labeling Validation (~15 minutes Experimental Group only). After completing use scenarios, the session moderator will complete a labeling validation study by having Experimental Group participants to review the IFU and/or device labeling and asking

content-related knowledge questions. Per FDA's request, results of the labeling validation portion of the study will be compared to existing data from the formative SureCRIC evaluation.

Human Study Data Analysis. Through direct observation as well as video/audio data reduction and analysis, usability test measures will be taken to evaluate the safe and correct performance of critical tasks and other essential tasks. Both performance data and participant feedback will be collected. Given the limited sample size and non-numerical nature of much of the data (e.g., subjective feedback), raw data presentation will be made. In compliance with FDA request, the study will present descriptive data only, as it is not designed for statistical analysis. Also, as discussed in the pre-submission meeting, no comparisons will be performed. A description and analysis of all usability issues will be presented along with root causes and implications for additional risk elimination or reduction.

Descriptive data only will be presented for each subject -A, B C, D, E, and F. The study is not designed for statistical comparisons between the Control (i.e., freehand) and Experimental (i.e., SureCRIC) groups. The following is an example of a summary data table that will be presented. Note that the data points presented in this table are placeholders used for demonstration purposely only and are not real data. As in previous studies [Bair 2015; Elliott 2010; Kristensen 2015; Lamb 2015], the "time to CTM identification" for each attempt will start when the participant first touches the subject's neck and end when the participant indicates that he/she has identified the CTM.

Example of Summary Data Table for Subject A (sample, not real, data)

Participant	Group	Success	VAS	Time to
			Visual Analog	CTM ID
			Scale	(sec)
1	Control	Υ	3	20
2	Control	Υ	9	17
3	Control	N	2	23
4	Control	N	8	19
5	Control	Υ	7	30
6	Control	N	5	35
7	Control	Υ	6	17
8	Control	Υ	4	18
9	Control	N	3	28
10	Control	N	8	23
Control Total / Average		5/10 (50%)	5.5	23
		success		
Participant	Group	Success	VAS	Time to
				CTM ID
				(sec)
11	Experimental	Υ	2	25
12	Experimental	Υ	3	19
13	Experimental	Υ	0	38
14	Experimental	N	4	22
15	Experimental	N	5	40

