16	Experimental	Υ	7	15

17	Experimental	Υ	3	28
18	Experimental	Υ	6	33
19	Experimental	Υ	3	26
20	Experimental	Υ	6	30
Experimental Total / Average		8/10 (80%)	4	27.6
		success		

Human factors data will be presented in both tabular and paragraph form. These will include data on critical and non-critical tasks, subjective feedback, and labeling comprehension information. A description and analysis of all use errors and difficulties that could cause harm will be provided along with root causes of the problems and implications for additional risk elimination or reduction.

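### Does it matter that the plan leaves open whether a failed CTM identification is debriefed as a critical error before labeling validation?

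*Combined protocol and SAP*

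**What the plan says.** Section III.1 (Human Study), step 4, has an expert judge each attempt, for level and for midline placement. This person "will indicate to the NCHFH staff (but not the participant) whether the popsicle stick is at the level of the CTM". A later sentence in the same step adds: "The medic will not be informed of the success or failure of their identification attempt until the end of their involvement in the study".

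In step 5, moderators "follow up with participants on any critical errors, close calls, or confusion/difficulty observed during task completion", so as to learn the user's view of the cause. Step 6 follows for SureCRIC users only: "After completing use scenarios, the session moderator will complete a labeling validation study by having Experimental Group participants to review the IFU". Section I.1 (Background) lists the same order: "5) semi-structured interviews and critical error debriefing; 6) completion of knowledge tasks and labeling validation (SureCRIC group only); and 7) compensation arrangement".

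The Human Study Data Analysis text promises: "A description and analysis of all use errors and difficulties that could cause harm will be provided along with root causes of the problems". Section I.2 (Purpose of the Study) places the interview and labeling material under the secondary endpoints: "post-participation human factors data will also be collected, as well as data from labeling validation".

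The available text neither defines a critical error or critical task nor says whether a failed identification is one.

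**The concern.** The primary endpoint is pass or fail on finding the CTM, and one overall objective is use of the device with few critical errors. A reader would expect the plan to say whether a fail is a critical error. Either answer seems to cause trouble.

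- **If a fail is a critical error**, step 5 must ask the user why a particular attempt failed. A SureCRIC user then learns the result with step 6 still to come, apparently against the non-disclosure rule. Labeling answers, which are to be set against formative data at FDA's request, would come partly from users who have just been told they failed.
- **If it is not**, a confident but wrong identification with no close call and no visible hesitation triggers no follow-up. The report would show the failure but hold no user's explanation of it. Asking later looks impossible, because Section II.5 says that after consent "there will be no connecting information between the person and their participant number or subject number".

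At stake would be the completeness of the root-cause account for failures of the device's intended use, and the cleanness of the labeling data.

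**Working it through.** The plan states no sample-size, power or error-rate figure, so there is nothing of that kind to reproduce. The check sets the passages against one another and then gauges scale.

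**1. What is already recorded when step 5 starts.** All six attempts belong to step 4. The verifier's judgement, the confidence rating and the time are taken attempt by attempt. Step 5 comes after the last attempt, so no disclosure there can alter the primary endpoint, the VAS or the time data.

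**2. The branch where a fail is a critical error.** The non-disclosure rule is breached only if the debrief conveys the verdict. Three features of the text leave room to avoid that:
- The interview is semi-structured, and a moderator can ask how a site was chosen without saying whether it was right.
- Step 6 is tied in its own wording to completion of the scenarios. Its place after step 5 comes from the numbering.
- The end of a medic's involvement is not defined. The rule sits within step 4, next to the sentence on examining the subjects one after another, so preventing feedback between attempts is a plausible purpose.

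Even if a verdict does slip out, step 6 asks what the IFU and labels say. Nothing in the documents suggests that knowing of a failure changes factual answers of that kind. Opinions given in the rest of step 5 are more open to influence.

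**3. The branch where it is not.** The analysis text promises root causes and does not say they must be the user's own account. The same section names direct observation and review of the recordings as sources, alongside participant feedback. SureCRIC users are also asked in step 5 about perceived difficulty, hard tasks and training, whether or not an error was seen. Each attempt in both arms carries a confidence rating. A failure-specific user account may be missing in either arm, but that is thinner evidence and does not contradict the promise.

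**4. Scale.** Section I.1 gives 24 medics, half using SureCRIC, and six subjects:

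- SureCRIC users: 24 / 2 = 12; attempts: 12 × 6 = 72.

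The documents give no real failure rate (the table values are placeholders), so the rate f is assumed. Attempts are treated as independent.

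| f | Expected failures, 72f | P(user has at least one) = 1 − (1 − f)^6 | Expected users, 12 × P |
|---|---|---|---|
| 5% | 3.6 | 0.265 | 3.2 |
| 10% | 7.2 | 0.469 | 5.6 |
| 20% | 14.4 | 0.738 | 8.9 |

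At f = 5% the chance of at least one failure in the arm is 1 − 0.95^72 = 0.975, so the unstated case will very probably occur.

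Failures lacking a user account, under the second branch, depend on q, the share showing visible difficulty (also assumed). For 4 to 14 failures the number is (1 − q) times that: 4 to 14 at q = 0, 2 to 7 at q = 0.5, and none at q = 1. The range is wide because neither input is documented.

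**The case for a change.** The best case for a change is that it would be cheap, and that the plan leaves moderators to choose. Two moderators could handle the same failure differently, one naming it and one not. Disclosure that depends on having failed is not neutral. General open-ended questions cannot recover the reason for a failure the user does not know about. A wrong site is a failure of the intended use, which is where a human factors report most needs the user's explanation. Once the medic leaves, the broken link to the participant number makes a later call impractical.

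Much of this stands as description: the term is undefined, the timing of disclosure is unstated, and a consistent approach across moderators is better than an improvised one. It does not show that a study run as written goes wrong. Section II.5 concerns confidentiality and does not close off the account, since the plan has medics learn nothing of their results before the end of involvement, when they can still comment on site. The proposed remedy of a scripted question on every attempt also has a price. At an assumed one minute each, six questions take 6 of the roughly 15 minutes in step 5 and displace open-ended feedback that the plan also wants.

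**Conclusion.** No change to the plan follows. This is a gap in session detail that moderators can fill sensibly, for example by keeping the debrief neutral on outcome and leaving disclosure and any failure-specific questions until last. The text permits that already.

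The primary endpoint, confidence and time data are untouched under any reading. The possible loss is a failure-specific user account for somewhere between none and about 14 of 72 SureCRIC attempts, assuming failure rates of 5% to 20%, with a similar gap possible in Control. Observation, recordings and the confidence rating remain in both arms, and general device feedback in the SureCRIC arm. The ordering question touches only the SureCRIC arm, because Control has no step 6. The study is descriptive and plans no group comparison, so no estimate or test depends on the answer.

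The conclusion rests on two judgements: that root causes may be drawn from sources other than the user, as the analysis text allows, and that factual labeling answers are little affected by knowing of a failure, which the documents neither support nor contradict.

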# 2 Methods and Data Analysis (Manikin Study)

The study will be a single-arm, open label study. Each of the participants will perform three cricothyrotomy procedures on a manikin. Each procedure will be performed with the SureCRIC and one of three representative cricothyrotomy kits. Participants in the manikin study will complete study sessions that will consist of the following:

- 1. Signing of Documents and Pre-Evaluation Interview (~5 minutes). Prior to study participation, relevant information on clinical experience will be collected from all participants. Sample data points include handedness, years of and nature of clinical experience, cricothyrotomy training with various approaches and kits, and previous cricothyrotomy performance. Upon arrival, participants will be asked to sign an informed consent form that describes participant's role in the evaluation, explains risks involved and consents to the use of audio and video recordings for analysis purposes. Participants will also be asked not to disclose any information about the product or materials they see during the training and evaluation.
- 2. Device Training (approximately 60 minutes). Participants will be introduced to each of the three cricothyrotomy kits as well as the SureCRIC and allowed to practice use on a manikin. SureCRIC training will consist of a review of the Instructions for Use (IFU) and supervised practice following a brief introduction to the device and procedure. A copy of the IFU is attached. Training with the three cricothyrotomy kits will include a review of the kit components and the IFU, and an opportunity to practice kit use, including with the SureCRIC, on a manikin model. Training will be conducted by [name]. Audio and video recording will be utilized for reference and use in data reduction and analysis (if applicable). Cameras will be positioned on tripods so as not to interfere with the training.

After completion of the training, the Human Factors Center will individually interview each participant using open-ended questions to garner subjective feedback on the training and instructional materials, as well as preparedness to perform SureCRIC-aided procedures.

3. Decay Period (minimum 60 minutes). After training, participants will be removed from the facility for a minimum of 60 minutes. Participants will then report to the testing facility at an agreed-upon time.

4. Usability Testing (approximately 30 minutes). After returning to the testing facility, participants will utilize the SureCRIC to perform various scenarios. A *Nasco Life/Form Cricothyrotomy Simulator* will be placed at the head of a table, fitted with a laryngeal insert, and covered with elastomeric "skin." The tool kit and packaged SureCRIC will be placed by the simulator. A new laryngeal insert and skin will be used for each scenario.

Manikin scenarios will include the following:

- Scenario #1: Direct percutaneous approach with Rusch QuickTrach Cricothyrotomy Kit
- Scenario #2: Seldinger approach with Melker Emergency Cricothyrotomy Catheter Set
- Scenario #3: Direct scalpel incision with North American Rescue Tactical Crickit

Each session will be observed by at least one Human Factors Center moderator, who will only be present to observe and give instructions and will not help participants with task completion in any way. Audio and video recording will be utilized for post-hoc data analysis. NCHFH staff will observe each manikin procedure focusing on usability and potential interference of the SureCRIC with the cricothyrotomy tools. NCHFH staff will additionally observe performance of critical tasks and essential tasks, focusing on the steps up to and including the step where the SureCRIC is removed from the manikin.

- 5. Semi-structured Interviews and Critical Error Debriefing (~15 minutes). Human Factors Center moderators will follow up with participants on any critical errors, close calls, or confusion/difficulty observed during task completion to determine the participant's perspective on the root cause of the error(s). Feedback will also be collected regarding perceived difficulty and usability of the device and IFU. Time is allotted for the moderator to ask the participants open-ended questions regarding their overall impressions of the SureCRIC, whether any tasks were particularly difficult to perform, whether training was adequate and how it might be improved, use of instructions during testing, and thoughts about SureCRIC use in the field. Participants will report on interference of the SureCRIC with his/her intended use of the cricothyrotomy tools.
- 6. Labeling Validation (~15 minutes). After completing use scenarios, the session moderator will complete a labeling validation study by having participants to review the IFU and/or device labeling and asking content-related knowledge questions. Per FDA's request, results of the labeling validation portion of the study will be compared to existing data from the formative SureCRIC evaluation.

Manikin Study Data Analysis. Through direct observation as well as video/audio data reduction and analysis, usability test measures will be taken to evaluate the safe and correct performance of critical tasks and other essential tasks. Both performance data and participant feedback will be collected. Given the limited sample size and non-numerical nature of much of the data (e.g., subjective feedback), raw data presentation will be made. In compliance with FDA request, the study will present descriptive data only, as it is not designed for statistical analysis. A description and analysis of all interference and usability issues will be presented along with root causes and implications for additional risk elimination or reduction.

